## **6. GENERAL ANALYSIS DEFINITIONS**

### **6.1 TREATMENT(S)**

In this Phase I trial, treatments are not randomized. Different dose levels of BI 754091 will arise in phase Ia and there is only one dose level in the 4 cohorts of phase Ib. Data of phase Ia and phase Ib will be displayed separately. In addition, for both phase Ia and phase Ib, data will be presented for all cohorts separately.

For phase Ia, the initial trial medication (i.e. dose level) assigned at the beginning of the first treatment cycle will be used as label of the analysing treatment.

Table 6.1: 1 Definition of analysing treatment periods for safety analysis

Analysing Treatment Period	Start Date	Stop Date
Screening	Date of informed consent	Date/Time of the first administration of trial treatment
On-treatment	Date/Time of the first administration of trial treatment	Date of the last administration of trial treatment + 30 days (residual effect period)
Follow-up	Date of the last administration of trial treatment + 31 days	Date of the last per protocol visit

Note: a 30-day residual effect period (REP) is defined for this trial.

For safety analyses, AEs will be classified to one of the following time periods: “Screening”, “On-Treatment” or “Follow-up.” This will be applied for all adverse events. Detailed rule for assigning AEs to these time periods are listed below:

- If the date of informed consent  $\leq$  AE onset date  $<$  date/time of first administration of BI 754091, then the AE is assigned to “Screening”;
- If date/time of first administration of BI 754091  $\leq$  AE onset date  $\leq$  date of last administration of BI 754091 + 30 days, then the AE is assigned to “On-Treatment”;
- If AE onset date  $>$  date of last administration of BI 754091 + 30 days, then the AE is assigned to “Follow-up”

### **6.2 IMPORTANT PROTOCOL DEVIATIONS**

According to (1) important safety protocol deviations (PDs) are those that potentially affect the rights or safety of study subjects. Important PDs are those that can potentially influence the primary outcome measure(s) for the respective patients in a way that is neither negligible nor in accordance with the study objectives.

No per protocol set is defined for this phase I trial, but patients with important protocol deviations (iPD) will be identified and reported in the clinical trial report (CTR). Potential Important PDs are defined in [Table 6.2: 1](#). The final list of important PDs will be confirmed at the last report planning meeting (RPM) before DBL.

Covid-19 related important and non-important PDs will be listed.

Table 6.2: 1 Important protocol deviations

Category / Code		Description	Comment / Example	Excluded from	Automatic/ Manual
A		Entrance criteria not met			
	A1.1	Patients potential for pregnancy or < 18 years	Inclusion criteria 2, 7 or 8 not met	None	Automatic
	A1.2a	Phase Ia - Patients do not have a histologically confirmed diagnosis of advanced, unresectable, and/or metastatic solid tumours (any type).	Inclusion criteria 3 not met during Phase Ia	None	Automatic
	A1.2b	Patients do not have measurable lesions according to RECIST v1.1 and iRECIST or life expectancy <12 weeks after start of treatment.	Inclusion criteria 3, 4, 6 not met	None	Automatic
	A1.3a	Phase 1a - Patients with PD-1 experience do not have a minimum of 60 days between the last dose of the previous PD-1 and Cycle 1 Day 1 of BI 754091 treatment.	Inclusion criteria 3 not met during Phase Ia	None	Automatic
	A1.3b	Phase 1b - patients who are anti-PD-1 naïve but have failed conventional treatment (excluding anti-PD-1 treatment), or for whom no therapy of proven efficacy exists, or who are not amenable to standard therapies.	Inclusion criteria 4 not met during Phase Ib	None	Automatic
	A1.4	Eastern Cooperative Oncology Group (ECOG, R01-0787) score > 1	Inclusion criteria 5 not met	None	Automatic
	A2.1	Major surgery performed within 12 weeks prior to first trial treatment or planned within 12 months after screening	Exclusion criteria 1 met	None	Automatic

Table 6.2: 1 Important protocol deviations (cont.)

Category / Code	Description	Comment / Example	Excluded from	Automatic/ Manual
A	Entrance criteria not met			
	A2.2	Intake of restricted medications or any drug considered likely to interfere with the safe conduct of the trial	Exclusion criteria 2 met	None Automatic
	A2.3	Previous enrolment in this trial	Exclusion criteria 3 met	None Automatic
	A2.4	Use of investigational or antitumour treatment within 30 days prior to the initial administration of BI 754091	Exclusion criteria 4 met	None Automatic
	A2.5	History within the last 5 years of an invasive malignancy other than the one treated in this trial. Refer to protocol for the exception.	Exclusion criteria 5 met	None Automatic
	A2.6	Untreated brain metastasis(es) that may be considered active.	Exclusion criteria 6 met	None Automatic
	A2.7	Inadequate organ function or bone marrow reserve as demonstrated by the laboratory values in CTP Section 3.3.3	Exclusion criteria 7 met	None Automatic
	A2.8	Improper cardiac criteria according to CTP Section 3.3.3	Exclusion criteria 8 met	None Automatic
	A2.9	History of pneumonitis within the last 5 years	Exclusion criteria 9 met	None Automatic
	A2.10	History of severe hypersensitivity reactions to other mAbs	Exclusion criteria 10 met	None Automatic
	A2.11	Immunosuppressive corticosteroid doses (>10 mg prednisone daily or equivalent) within 4 weeks prior to the first dose of BI 754091	Exclusion criteria 11 met	None Automatic
	A2.12	Active autoimmune disease or a documented history of autoimmune disease, except vitiligo or resolved childhood asthma/atopy	Exclusion criteria 12 met	None Automatic

Table 6.2: 1 Important protocol deviations (cont.)

Category / Code	Description	Comment / Example	Excluded from	Automatic/ Manual	
A					
	A2.13	Known history of human immunodeficiency virus infection or an active hepatitis B or C virus infection	Exclusion criteria 13 met	None	Automatic
	A2.14	Interstitial lung disease	Exclusion criteria 14 met	None	Automatic
B		Informed consent			
	B1	Informed consent not available/not done	Inclusion criteria 1 not met	None	Automatic
	B2	Informed consent too late	Inclusion criteria 1 not met- Informed consent obtained later than the initiation of treatment	None	Automatic
C		Trial medication			
	C1.1	Non-compliance with BI 754091 per protocol	Incorrect trial medication dose taken or wrong dose schedule, i.e. wrong infusion time; this will be the decision at MQRM	None	Automatic and manual
	C1.2	Discontinuation of trial medication not following the protocol	Decision at MQRM	None	Automatic and manual
D		Concomitant medication			
	D1.1	Prohibited medication use	Review concomitant medications for prohibited medication use; also refer to Section 4.2.2.2 of the protocol	None	Manual
E		Study Specific			
	E1	Incorrect study procedure(s) performed.	Any deviation from protocol not defined above deemed important to document in study report by trial team.	None	Manual

**Note:** MQRM – Medical and Quality Review Meeting

### **6.3 SUBJECT SETS ANALYSED**

#### **Screened Set:**

This patient set includes all patients who have signed the informed consent. The screened set will be used for patient disposition tables.

#### **Treated Set (TS):**

This patient set includes all patients who were documented to have received at least one dose of BI754091. The TS is used for both efficacy analyses and safety analyses.

#### **MTD set:**

This patient set includes all patients enrolled in a Ia dose finding cohort of the trial who were not replaced within the MTD evaluation period

**PK Analysis Set (PKS):**

This patient set includes all patients in the TS who provide at least one evaluable observation for at least one PK endpoint and no PK relevant protocol deviations. PKS will be used for statistical pharmacokinetical analyses.

**6.5 POOLING OF CENTRES**

This section is not applicable because centre/country is not included in the statistical model.

**6.6 HANDLING OF MISSING DATA AND OUTLIERS**

Missing or incomplete AE dates are imputed according to BI standards.  
Missing data and outliers of PK data are handled according to (2).

Potential outliers will be reported and analysed as observed. In general, missing data not discussed in (2) and BI standards will not be imputed unless required for the following analyses and definitions. Then the rules as described below apply.

**1) Change of laboratory values from baseline**

Laboratory values at baseline: For missing laboratory data at cycle 1 day 1 (before the first administration of any study medication) the data of preceding visits will be used if available.

**2) Definition of on-treatment period and actual treatment**

Date of permanent discontinuation of study medication: All reasonable efforts should be undertaken during the study to obtain the dates of permanent discontinuation of study medication. However, if the date of the very last administration is missing this will be imputed with:

- If only month and year are given, the last day of the month will be used for imputation
- If only the year is given, the 31st of December of this year will be used for imputation

If the imputed date leads to a date that is later than the date of the EOT visit, then the imputed date is the date of the EOT visit. If the imputed date leads to a date that is later than the death date, then the imputed date is the date of death.

### **3) Partial death dates**

If a partial (year and month) death date is reported, the date will be imputed with the end of the month for the analysis of PFS. This is in line with the imputation of partial dates for the analysis of AEs.

### **4) Partial or missing start date of subsequent anti-cancer therapy/subsequent radiotherapy**

If the day of the start date of subsequent systemic therapy/subsequent radiotherapy is missing, then the 1st of the month will be imputed unless this leads to a date before the stop date of study medication. In this case the stop date of study medication +1 day will be imputed.

If day and month, or day and month and year are missing, it will be distinguished whether the start date of subsequent systemic therapy/subsequent radiotherapy is required for censoring of PFS or for other descriptive statistics:

- For censoring of PFS or DoR: If only the year is reported, the 1st of January of this year will be imputed unless this leads to a date before the stop date of study medication. In this case the stop date of study medication +1 day will be imputed. In case of a completely missing start date of subsequent anti-cancer therapy/subsequent radiotherapy and the patient did not have any post-baseline tumour assessment or did not progress or die, the PFS of this patient will be censored at the day of first administration of BI 754091. Additionally, all imputed start dates of subsequent anti-cancer therapy/subsequent radiotherapy should be before death date, if available.
- For descriptive statistics: Dates will not be imputed if more than only the day of the date is missing.

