## **5. ENDPOINTS(S)**

### **5.1 PRIMARY ENDPOINT(S)**

The primary objective of this study is to determine the safety and tolerability of BI 754091 as reflected by the primary endpoint MTD.

The primary endpoint of the Phase Ia dose-escalation portion of the trial is:

- Number of patients experiencing Dose Limiting Toxicities (DLTs) graded according to CTCAE Version 4.03, observed in the first cycle (3 weeks) in order to meet the objective of assessment of the MTD of BI 754091.

The number of patients with DLTs during the MTD evaluation period will be used to determine the MTD. The MTD is defined as the highest dose with less than 25% risk of the true DLT rate being above 33% during MTD evaluation period. For definition of DLTs, see CTP Section 4.1.5. The MTD evaluation period is defined as the first three weeks after a first administration of trial medication to BI 754091.

Patients who were replaced during the MTD evaluation period will not be considered for MTD determination. Those patients that have completed the MTD evaluation period without having been replaced will be referred to as patients evaluable for MTD determination (MTD set).

In addition, the primary endpoints of the Phase Ib dose-expansion portion of the trial are:

- Number of patients with DLTs observed during the entire treatment period, from the first infusion of study treatment to the date of last study treatment administration plus 30 days. See treatment period definition in [Table 6:1:1](#).
- Confirmed objective Response (OR), defined as the best overall response of confirmed complete response (CR) or partial response (PR) according to RECIST v1.1 assessed by the Investigator, where the best overall response is the best time point response recorded from the first administration of BI 754091 until the earliest of disease progression according to RECIST v1.1, death or last evaluable tumor assessment before start of subsequent anti-cancer therapy, loss to follow- up or withdrawal of consent.

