Death but no progression, no missed radiological assessment window* prior to death	Event	Date of death
Death without progression, but one or more consecutively missed radiological assessment window* prior to death	Censored	Date of last evaluable radiological assessment prior to missed assessments
Initiation of subsequent anti-cancer therapy		
Subsequent anti-cancer therapy started before progression or death	Censored	Date of last radiological assessment before subsequent anti-cancer therapy
No baseline and/or post-baseline imaging and subsequent anti-cancer therapy started prior to death	Censored	First treatment administration

\* Windows for radiological assessments are defined in [Table 6.7: 1](#)

[figure not shown]

---

Proprietary confidential information © 2021 Boehringer Ingelheim International GmbH or one or more of its affiliated companies

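### When only the month of subsequent therapy is known, its start is imputed without using the progression date, so progression followed by a switch in that month can become a PFS censoring

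*SAP*

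**What the plan says.** SAP 6.6 item 4 covers incomplete start dates of subsequent anti-cancer therapy or radiotherapy.

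- **Day missing.** The 1st "of the month will be imputed unless this leads to a date before the stop date of study medication". The lower limit is then applied: "In this case the stop date of study medication +1 day will be imputed".
- **Year only, for censoring PFS or duration of response.** 1 January, with the same lower limit.
- **Upper limit.** "Additionally, all imputed start dates of subsequent anti-cancer therapy/subsequent radiotherapy should be before death date, if available".
- **Date wholly missing.** PFS is censored at first dose for a patient who "did not have any post-baseline tumour assessment or did not progress or die". This is the only branch that looks at progression.

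Table 5.2.2.2: 1 in SAP 5.2.2.2 has a row for "Subsequent anti-cancer therapy started before progression or death". Its outcome is a censoring at the last scan before that therapy. Without that row, progression with no missed scan window is an event on the scan date.

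The stop date is not defined in item 4. Item 2, on the date of permanent discontinuation, says: "However, if the date of the very last administration is missing this will be imputed with". That points to the last infusion.

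**The concern.** For a partial date, the imputed start is the earliest day that the known part and the stop date allow. The progression date is normally known, but it does not enter. Infusions are 21 days apart, so a scan taken just before the next infusion falls about 3 weeks after the last one. A lower limit at stop date + 1 then lies well before the progression scan and does not preserve the order of events.

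The patients affected are those who progress and change treatment quickly. Their events are replaced by earlier censorings, and that censoring is related to outcome. The rule is also uneven. Read literally, a patient with documented progression keeps the event if nothing is known about the switch date, but can lose it if the month is known.

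**Working it through.** The plan states no figure that depends on this rule, so there is nothing to reproduce. The check applies the rule as written.

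**Inputs from the documents.** The imputation rule (SAP 6.6 item 4), the censoring rows (SAP Table 5.2.2.2: 1), 21-day cycles (Protocol synopsis), and scan due days 43 and 85 (SAP Table 6.7: 1).

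**Assumptions.** The stop date is the last infusion. L is the number of days from last infusion to progression scan. G is the number of days from progression to the true switch. Progression falls evenly over 2018–2021 (1,461 days, 48 months).

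**One patient.** First dose 1 April 2019. Scan without progression on 13 May (Day 43). Last infusion 3 June (Day 64). Progression scan 24 June (Day 85). New therapy 27 June, recorded only as June 2019. Since 1 June precedes 3 June, the rule imputes 4 June. That is before 24 June, so an event at Day 85 becomes a censoring at Day 43.

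**When the order flips.** The imputed start is the 1st if that is not before the stop date, otherwise stop date + 1. The event is lost when the imputed start is before progression.

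- If the 1st is used, the event is lost unless progression is itself dated the 1st, which is a tie.
- If stop date + 1 is used, it equals progression − L + 1, so the event is lost when L ≥ 2.
- L = 1 gives a tie, except when the last infusion was on the 1st (about 3% of calendar positions).
- L ≤ 0, with the last infusion on or after progression: 0% lost.

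For any L ≥ 2, including 21, the loss therefore needs only that progression and switch share a month and that progression is not on the 1st. A month of m days has m − G − 1 such dates (none if negative). For G = 7, 14 and 21 the share is [1,461 − 48(G + 1)] / 1,461. For G = 28, only 30-day months (16 × 1 date) and 31-day months (28 × 2 dates) contribute.

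| Gap G (days) | Lost, of all missing-day dates | Lost, if progression and switch share a month |
|---|---|---|
| 7 | 1,077/1,461 = 74% | 96% |
| 14 | 741/1,461 = 51% | 94% |
| 21 | 405/1,461 = 28% | 89% |
| 28 | 72/1,461 = 5% | 62% |

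**Overall size.** For gaps spread evenly over 7–35 days the average loss is 30%. The share of switch dates with a missing day is not given. Assuming 5%, 10% or 20%, the loss is 1.5%, 3% or 6% of progression events among switchers. Of 25 such events that is about 0.4, 0.75 or 1.5.

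**Effect on the curve (invented data).** Take 30 patients with progressions at Days 43, 85, 127 and 169 in 12, 6, 4 and 3 patients, and 5 censored at Day 232. Kaplan-Meier PFS at Day 85 is (18/30) × (12/18) = 40%. Mis-ordering 2, 4 or 6 events, split between Days 43 and 85, gives:

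- 2 events: (18/29) × (12/17) = 44%
- 4 events: (18/28) × (12/16) = 48%
- 6 events: (18/27) × (12/15) = 53%

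That is roughly 2 percentage points per lost event. An imputed date at the earliest allowed day can remove an event but cannot create one, so from the lost progression onward the curve can only rise.

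**The case against.** **The lower limit often protects the event.** The flow-chart footnotes and Protocol 5.2.1 allow treatment past initial progression. Due days 43 and 85 are also infusion days, so dosing on the scan date is possible. This stands: the percentages apply only when the last infusion was at least 2 days earlier. If half of patients were dosed on or after progression (an assumption), the 30% average becomes about 15%.

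**The stop date is undefined.** Protocol 6.2.3.1 also treats discontinuation as a decision. If the stop date were the decision date, the limit would usually fall on or after progression and most events would survive. Item 2 favours the last infusion but does not settle it.

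**The effect is small.** PFS is a descriptive secondary endpoint, Protocol 7.2 plans no hypothesis test, and no sample size depends on it. This also stands.

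A reader might infer two stronger points that the documents do not support.

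- *That the primary objective response is damaged too.* The response window in SAP 5.1 closes at the earliest of progression, death or the "last evaluable tumor assessment before start of subsequent anti-cancer therapy". For a patient who progressed and then switched, a confirming scan would have to fall between the imputed start and progression. Scheduled scans are 6 or 9 weeks apart, so none fits into the 3 weeks after the last infusion. A patient who stopped without progression might lose a scan, but using the progression date would not help that patient.
- *That year-only dates make the problem large.* Read literally, the rule flips 92–98% of them for gaps of 28 down to 7 days. Nothing suggests that such dates are common, since Protocol 4.2.2 has new anti-cancer treatment recorded on its own eCRF page. The year alone also says little about the true order.

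**Conclusion.** The point holds for dates with a missing day, on two conditions: the stop date is the last infusion, and that infusion was at least 2 days before the progression scan. A documented progression followed by a switch in the same month then becomes an earlier censoring, except when progression is dated the 1st. No other visible part of the SAP restores the order.

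The loss rates in the table are conditional on these assumptions and are not forecasts for the trial. The net effect is probably small and rests on a share of partial dates that the documents do not give. It has one direction, towards longer PFS, and is greatest for patients who switch soonest. That justifies correcting the text. No conclusion about objective response, and no formal inference, is affected.

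**What to change.** In SAP 6.6 item 4:

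1. Define the stop date of study medication as the date of last administration.
2. Where the day is missing and documented progression falls in the reported month, impute the latest of the 1st of the month, stop date + 1 and progression date + 1, not beyond the end of that month or death. State that a start on the progression date is not before progression, so that the month-end cap leaves the event in place. In the example above, the imputed start becomes 25 June and the event stays at Day 85.
3. For year-only dates, do not move the start past progression automatically. A patient who stopped in January, switched in February and progressed in November would otherwise have progression on the new therapy counted against the study drug. Query the site for the month or for the order of progression and switch, and report PFS under both orderings as a sensitivity analysis.

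The cost is a few sentences, a short change to the derivation code, and queries for the year-only cases. PFS may read slightly shorter, and a progression that truly followed a switch within the same month would be counted as an event.

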4.2.2.2 Prohibited concomitant medications

- No other investigational therapy or anticancer agent should be given to patients. If such agents are required for a patient, then the patient must first be withdrawn from the trial.
- Immunosuppressive medications including, but not limited to systemic corticosteroids at doses exceeding 10 mg/day of prednisone or equivalent, methotrexate, azathioprine, and tumour necrosis factor-alpha blockers are prohibited. Use of immunosuppressive medications for the management of investigational product-related AEs or in patients

with contrast allergies is acceptable, and does not necessarily warrant immediate treatment discontinuation. In addition, use of inhaled, topical, intranasal corticosteroids or local steroid injections (e.g., intra-articular injection) is permitted. Temporary uses of corticosteroids for concurrent illnesses (e.g., food allergies, CT scan contrast hypersensitivity) are acceptable upon discussion with the Medical Monitor.

- Live attenuated vaccines during the trial through 30 days after the last dose of investigational product are prohibited.
- Herbal preparations/medications are not allowed throughout the trial unless agreed to by the Principal Investigator. These herbal medications include, but are not limited to: St. John's wort, kava, ephedra (ma huang), gingko biloba, dehydroepiandrosterone (DHEA), yohimbe, saw palmetto, and ginseng. If instructed by the Principal Investigator, patients should stop using these herbal medications 7 days prior to first dose of BI 754091.

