**PFS according to RECIST v1.1:**

For patients with 'event' as outcome for PFS:

- PFS [days] = date of outcome – date of first treatment administration + 1

For patients with 'censored' as outcome for PFS:

- PFS (censored) [days] = date of outcome – date of first treatment administration + 1

A patient has an evaluable response assessment if CR, PR, stable disease (SD), or progressive disease (PD) according to RECIST v1.1 has been assigned by the investigator. The censoring rules and applicable dates of outcome are specified in Table 5.2.2.2: 1 below.

If patients would have their radiological examinations over a number of days, i.e. target lesions assessed on day x, non-target lesions assessed on day y and new lesion (if applicable) on day z, the earliest date of the multiple assessments should be considered.

Table 5.2.2.2: 1 Censoring rules for progression-free survival according to RECIST v1.1

Situation	Outcome	Date of outcome
No baseline radiological assessment		
Patient with death on or before first planned post-baseline radiological assessment ( $\leq$ Day 64)	Event	Date of death
Patient without death or patient with death after first planned post-baseline radiological assessment ( $>$ Day 64)	Censored	First treatment administration
Without post-baseline radiological assessments		
Vital status is unknown or patient is known to be alive	Censored	First treatment administration
Death prior to or on the first planned post-baseline radiological assessment ( $\leq$ Day 64)	Event	Date of death
Death beyond the first planned post-baseline radiological assessment ( $>$ Day 64)	Censored	First treatment administration
With baseline and post-baseline radiological assessments BUT no other anti-cancer therapy		
Alive and not progressed	Censored	Date of last evaluable radiological assessment
Progressed, no missed radiological assessment window* prior to progression	Event	Date of radiological assessment of progression

Table 5.2.2.2: 1 Censoring rules for progression-free survival according to RECIST v1.1  
(cont.)

Situation	Outcome	Date of outcome
Progressed, but one or more consecutively missed radiological assessment window* prior to progression	Censored	Date of last evaluable radiological assessment prior to missed assessment (or first treatment administration if no post-baseline assessment prior to missed assessment)

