#### Imaging time windows:

Time windows and visits will be calculated to determine the planned day of tumour measurement and response status, based on the protocol-specified tumour imaging schedule.

For the presentation of tumour response data which will follow a calculated visit approach

based on the protocol specified tumour imaging schedule. Imaging will be performed at screening and every 6 weeks after BI 754091 infusion (i.e. Week 6, 12, 18 ...etc.), then every 9 weeks after 6 months of treatment; image data will be slotted to Week 6, 12, 18 etc. based on their relative day (from start of treatment) and using a  $\pm 3$  week window (images taken in the first 3 weeks from start of treatment will be assigned to Week 6). If two or more images for a patient are assigned to one interval then the last assessment will be used to ensure progressive disease is not missed.

In order to identify whether consecutive imaging time points are missing for a given patient, a nominal time point (i.e. Week 6, 12, 18 ... etc.) will be assigned to each and every image. This is achieved by creating windows for every radiological response assessment. These windows are defined in [Table 6.7: 1](#).

Table 6.7: 1 Nominal time points and windows for imaging

Nominal time point (weeks from start of study medication)	Due date of scans (days)*	Window (days)
6	43	1 to $\leq$ 64
12	85	65 to $\leq$ 106
18	127	107 to $\leq$ 148
24	169	149 to $\leq$ 200
33	232	201 to $\leq$ 263
42	295	264 to $\leq$ 326
51	358	327 to $\leq$ 389
Etc., 9 week interval	Etc.	Etc.

\* The date of the first dose of study medication is Day 1

If a patient does not have an image in one of the windows described above, he/she will be considered to have missed an assessment for that time point.

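### A completely missing start date of later therapy resets PFS to Day 1, even for patients with evaluable scans and no progression or death

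*SAP*

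**What the plan says.** SAP 6.6 item 4 sets out what to do when the start date of later anti-cancer therapy or radiotherapy is incomplete.

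- **Day missing, or day and month missing.** The first of the month, or 1 January, is used. If that falls before the stop date of study medication, "In this case the stop date of study medication +1 day will be imputed".
- **Date completely missing.** If "the patient did not have any post-baseline tumour assessment or did not progress or die", then "the PFS of this patient will be censored at the day of first administration of BI 754091".

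The main PFS rules are in SAP Table 5.2.2.2: 1. If later therapy starts before progression or death, the censoring date is "Date of last radiological assessment before subsequent anti-cancer therapy". The other later-therapy row, "No baseline and/or post-baseline imaging and subsequent anti-cancer therapy started prior to death", is the one that censors at first administration.

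Protocol 4.2.2.2 adds: "No other investigational therapy or anticancer agent should be given to patients". A patient who needs such an agent must first be withdrawn.

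**The concern.** The two conditions in the completely-missing rule are joined by 'or'. The rule therefore covers patients without any post-baseline scan, and also any patient who neither progressed nor died, whatever imaging exists. A patient in the second group with several evaluable progression-free scans is treated as if never followed.

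Among patients with post-baseline scans and a completely missing date, the rule acts only on those without an event. Removing them from the risk set before the first possible event lowers the Kaplan-Meier curve. PFS is the secondary efficacy endpoint of Phase Ib, reported by cohort with about 30-40 patients planned in each, so a few patients can shift an estimate.

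**Working it through.** The plan gives no figure for this rule, so there is none to reproduce. The check compares the rules, works out the loss per patient, and then sizes the effect on assumptions.

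**1. The rules side by side**, for a patient with evaluable scans, no progression or death, and later therapy:

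| Start date of later therapy | PFS censored at |
|---|---|
| Known | last scan before the therapy (Table 5.2.2.2: 1) |
| Month and year, or year only | last scan before an imputed date that is never earlier than the stop of study medication |
| Completely missing | Day 1 |

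The lower bound used in the second row is equally available in the third.

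**2. Loss per patient.** The formula under "For patients with 'censored' as outcome for PFS" is date of outcome - date of first administration + 1. Censoring at first administration gives 1 day, or 1 x 12 / 365.25 = 0.03 months. Table 6.7: 1 states that "The date of the first dose of study medication is Day 1" and puts scans on Days 43, 85, 127, 169, 232, 295 and 358. Censoring at the last scan would give, for example:

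- Week 6: 43 days (1.41 months)
- Week 24: 169 days (5.55 months), so the rule discards 168 of 169 days
- Week 51: 358 days (11.76 months)

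**3. Effect on a cohort.** The following inputs are assumptions, not from the documents. Progression times are exponential with median 90 or 180 days and are detected at the next scheduled scan. At each scan there is a 5% or 10% chance of moving to later therapy without progression, independent of progression risk. Of those start dates, 25%, 50% or 100% are completely missing. Cohorts have 30 or 40 patients, with 2000 runs per setting. The true Day 169 PFS is 0.5^(169/90) = 27.2% or 0.5^(169/180) = 52.2%.

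| Median | Patients affected | SAP rule | Last-scan censoring | Rule below truth by |
|---|---|---|---|---|
| 90 days | 2-3% | 26.2-26.4% | 27.2-27.3% | 0.8-1.0 points |
| 90 days | 5% | 25.4-25.5% | 27.2-27.3% | 1.7-1.8 |
| 90 days | 9-10% | 23.2-23.5% | 27.0-27.2% | 3.7-4.0 |
| 90 days | 19% | 19.8-20.2% | 27.2-27.6% | 7.0-7.4 |
| 180 days | 4% | 50.8-51.2% | 52.0-52.4% | 1.0-1.4 |
| 180 days | 7-8% | 49.8-50.0% | 52.2-52.5% | 2.2-2.4 |
| 180 days | 14-16% | 47.1-47.6% | 52.2-52.4% | 4.6-5.1 |
| 180 days | 28% | 41.3-41.4% | 52.1-52.2% | 10.8-10.9 |

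**4. Sensitivity to the independence assumption.** In a second set-up, the affected patients' last scan was drawn at random from the scans before their own progression, so leaving was tied to prognosis. About 4-17% of patients were affected. The SAP rule was still below the truth (25.5-26.8% against 27.2%; 50.1-51.7% against 52.2%). Last-scan censoring was above it (27.8-30.2%; 52.8-55.3%). The direction of the rule's bias held in both set-ups; the near-absence of bias under last-scan censoring did not.

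**The case against.** The strongest reply is that this will rarely happen and matters little when it does. Even the year must be unknown, because a year alone triggers imputation. New anti-cancer treatment has its own eCRF page (protocol 4.2.2), and follow-up contact is at least every 12 weeks (6.2.3.3, 6.2.3.4). PFS is descriptive and no hypothesis is tested (7.2). All of this stands and limits the size of the point. It does not make the sentence right.

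A reader might infer more than the documents support:

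- **That the longest progression-free times are removed.** Nothing shows this; an affected patient may have only a Week 6 scan.
- **That every patient caught by the rule loses follow-up.** Patients without post-baseline scans lose no scan time, and for them Day 1 agrees with the later-therapy row of the table.
- **That later therapy cannot precede the stop of study drug.** Protocol 4.2.2.1 allows some palliative radiotherapy on treatment after Cycle 1. The ban on other anticancer agents is a rule, not a fact about the data, and SAP Table 6.2: 1 lists prohibited medication as a possible deviation. What remains is that the SAP's partial-date rules already make this assumption.
- **That three affected patients in 30 cost about 7 points.** With 11 of 30 event-free at 6 months and no other censoring, (11 - 3)/(30 - 3) = 29.6% against 36.7%. That needs all three to be event-free past 6 months. The simulation at 10% of 30 patients gives 3.8 points.
- **That it is enough to impute stop date + 1 and censor at the last scan on or before it.** SAP 6.6 item 2 treats the stop date as the last administration. With a last dose on Day 1 + 21 = Day 22, the imputed start is Day 23 and the first scan is due on Day 43. A clean Day 43 scan would be missed, and a progression seen on Day 43 could be turned into a censored observation.

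**Conclusion.** The point holds for one defined group: patients with a completely missing start date of later therapy, at least one evaluable post-baseline scan, and neither progression nor death. For them SAP 6.6 item 4 contradicts Table 5.2.2.2: 1 and is out of line with its own partial-date rules. It replaces observed progression-free time with 1 day and biases the Phase Ib PFS estimate downward.

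The illustrative drop in Day 169 PFS (5.55 months, close to 6) is 0.8-1.8 points when 2-5% of patients are affected. It is about 4 points at 9-10% under the 90-day median. These sizes rest on the assumed medians, switching rates and missing-date fractions. The real number affected is unknown and probably small. The sentence should be corrected, but it does not threaten the trial's main conclusions.

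**What to change.** Rewrite the completely-missing case in SAP 6.6 item 4 as follows:

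1. If there is no evaluable post-baseline assessment, censor at Day 1, as now.
2. If there is at least one evaluable post-baseline scan and no progression or death, censor at the last evaluable radiological assessment up to the end of study treatment. That means up to the later of stop date of study medication + 1 day and the end-of-treatment assessment. Use Day 1 only if no such scan exists.
3. Leave recorded progressions as the present sentence does; an imputed therapy date must not turn them into censored observations.
4. State the outcome for duration of response. The bullet announces both endpoints but gives only PFS for this case. The visible SAP has no derivation for duration of response, so the wording must be checked against the full text.
5. State what happens to a patient with post-baseline scans who died without progression. The present sentence is silent on this.

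The cost is a short SAP revision and a small program change. The new rule relies on later therapy starting after study treatment ends, which the partial-date rules already assume. Like any last-scan censoring, it can overstate PFS if leaving treatment is related to prognosis.
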